1.3.3 The Importance of 18F-FAPI PET/CT in Prognostic Prediction of Lung Cancer

There is a significant correlation between imaging features and tumor mutational burden (TMB), and imaging assessment can serve as an effective tool for predicting immune therapy response [26]. This combination not only improves the accuracy of efficacy prediction but also provides new insights for personalized treatment. However, as an emerging imaging technology, 18F-FAPI PET/CT still requires further research in predicting patient prognosis and treatment response.

Based on this, the present study adopted a prospective, multicenter research design to evaluate the diagnostic efficacy and prognostic value of 18F-FAPI PET/CT in lung cancer.

2 Objectives and Content of Clinical Research

2.1 Objectives of Clinical Research

The purpose of this study was to evaluate the diagnostic efficacy and prognostic value of 18F-FAPI PET/CT in lung cancer.

Primary endpoint: Diagnostic efficacy of 18F-FAPI PET/CT in lung cancer patients (sensitivity, specificity, accuracy)

secondary end points:

- ① Compare the diagnostic performance differences of 18F-FAPI PET/CT with CT, MR, and 18F-FDG PET imaging in clinical applications for lung cancer;
- ② Analysis of diagnostic differences in the subgroup of patients (pathological, genetic, etc.) using 18F-FAPI PET/CT;
- ③ Evaluation of 18F-FAPI PET/CT in predicting lung cancer prognosis.

2.1 Content of Clinical Studies

2.1.1 Evaluation of the Diagnostic Performance of 18F-FAPI PET/CT

This study aims to evaluate the sensitivity, specificity, and accuracy of 18F-FAPI PET/CT in lung cancer patients, providing a basis for clinical application. By performing 18F-FAPI PET/CT scans on lung cancer patients and collecting relevant data, the performance of this modality in early diagnosis, staging, and recurrence monitoring was analyzed. The goal is to provide a scientific basis for clinical decision-making in the diagnosis and treatment of lung cancer.

2.1.2 Comparative Study of 18F-FAPI PET/CT with Other Imaging Techniques (CT, MR, FDG PET/CT)

A comparative study of 18F-FAPI PET/CT versus conventional imaging modalities (CT or MR) or 18F-FDG PET/CT in lung cancer patients, evaluating the differences in tumor detection sensitivity, specificity, and accuracy among various imaging techniques. The study aims to clarify their advantages in clinical applications for lung cancer. The research will focus on analyzing the differences in tumor size, location, metastasis, and pathological characteristics among the imaging techniques, exploring the potential of 18F-FAPI PET/CT in improving diagnostic accuracy and early detection of lung cancer.

2.1.3 Diagnostic differences in the 18F-FAPI PET/CT analysis of lung cancer subgroups

Subgroup analysis was performed based on pathological type, stage, and molecular subtype, stratified by disease pathological type (adenocarcinoma/squamous cell carcinoma/small cell lung cancer), stage (early/advanced), and molecular subtype (EGFR mutation-positive, ALK-positive, ROS1-positive). The aim was to evaluate the differences in sensitivity and specificity of 18F-FAPI PET/CT across different patient populations. This study will help identify which specific types of lung cancer patients are more likely to benefit from 18F-FAPI PET/CT, thereby providing a basis for the development of individualized treatment plans.

2.1.4 Evaluation of 18F-FAPI PET/CT in Predicting Lung Cancer Prognosis

Based on TNM staging and PERCIST criteria, this study evaluates the post-treatment reassessment, efficacy prediction, and prognostic assessment (AUC comparison of PFS/OS) of 18F-FAPI PET/CT in lung cancer. The research will analyze the monitoring capability of 18F-FAPI PET/CT in assessing tumor response post-treatment

and its value in prognostic evaluation, aiming to provide clinicians with a more precise tool for assessing treatment efficacy. It tracks the time from diagnosis to specific events (e.g., CR, PR, SD, PD, recurrence, death) in lung cancer patients to identify influencing factors. Survival rates over time are plotted using Kaplan-Meier curves to visually compare survival differences across groups. Additionally, Cox proportional hazards model multivariate regression quantifies the contribution of factors such as age and pathological stage to survival risk, aiding clinical decision-making.

3 Mechanism of Action and Research Scope of 18F-FAPI PET/CT

18F (97% β^+ , $T_{1/2}=109.7$ minutes) is currently the most widely used radionuclide in PET/CT due to its chemical, physical, and nuclear properties, making it an ideal choice for peptide-based imaging. 18F-FDG is the most commonly used PET tracer in oncology, serving as the preferred modality for tumor diagnosis and therapeutic efficacy evaluation. However, 18F-FDG PET/CT exhibits relatively low sensitivity and specificity for tumors with low invasiveness, high differentiation, or mucinous tissue, while physiological uptake in organs such as the oropharynx and digestive tract often obscures tumor metabolism and uptake. Additionally, mediastinal and hilar lymph nodes still show a high rate of false positives on 18F-FDG PET, whereas 18F-FAPI PET/CT improves the specificity of lymph node diagnosis. Furthermore, compared to 68Ga-labeled tracers, 18F-labeled FAPI has better resolution potential due to its lower positron energy. Therefore, 18F-labeled FAPI holds significant clinical value and promising prospects.

4 Indications, Contraindications, and Precautions

4.1 Eligibility Criteria: Patients with suspected or confirmed lung cancer who have undergone 18F-FAPI PET/CT

4.2 Exclusion Criteria:

- (1) Concurrent presence of other active malignant tumors or a history of other malignant tumors within the past 5 years;
- (2) Severe uncontrollable diseases or active infections;
- (3) Ineligible participants for informed consent.
- (4) Pregnant and lactating women.

5 、 system design

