5.3 Subject Selection

5.3.1 Eligibility Criteria for Subjects

- (1) Patients with suspected or confirmed lung cancer
- (2) 18F-FAPI PET/CT has been performed.

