6.2 Subject Screening

Participants will sign an informed consent form prior to enrollment in this study. Investigators will explain the nature, purpose, and risks of the study and provide the participants with an informed consent form. Participants will be given sufficient time to consider the significance of the study before deciding whether to participate. Any modifications to the informed consent form must be notified and approved by the ethics committee prior to participant enrollment.

First, participants must undergo an informed consent process and sign an informed consent form. Subsequently, eligible subjects are screened from the target population according to the pre-established inclusion and exclusion criteria of this study, after which they may be considered for inclusion in the research.

Baseline data collection included general examinations, medical history, and laboratory tests conducted at the same hospital or external hospitals within one week prior to the signing of the informed consent form. Adverse events and concomitant medications were collected after the signing of the informed consent form.

history-taking

Conduct a detailed inquiry into the patient's medical history to clarify symptoms, signs, and prior medical history (e.g., tumor history, surgical history, biopsy history, radiotherapy history, chemotherapy history, family history,

allergy history, etc.), relevant laboratory tests, previous imaging findings (including plain radiography, ultrasound, CT, MRI, as well as 18F-FDG PET/CT, PET/MR, etc.), and recent pathological results (including tumor grading and Ki-67 index, etc.), along with the patient's follow-up medical records.

Image judgment criteria

The uptake of imaging agents in tissues or organs that normally do not take up such agents can be considered pathological. Typically, 18F-FAPI is rapidly cleared from the bloodstream. Taking 18F-FAPI as an example, radioactive distribution can be observed in the salivary glands, thyroid, liver, biliary tract, gallbladder, pancreas, adrenal glands, kidneys, intestines, collecting system, and bladder, with almost complete excretion through the biliary tract. There is minimal distribution of the radioactive imaging agent in brain tissue. Compared to the liver, if the uptake is significantly increased in a lesion, it is considered positive, suggesting malignant tumors. Generally, moderate intestinal distribution and non-focal intestinal uptake are considered non-pathological.

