7.3 Statistical Methods

Statistical analysis was performed using SPSS 17.0. The diagnostic sensitivity, specificity, and negative/positive predictive values were calculated using a four-cell table. The area under the ROC curve and the optimal cutoff value (SUV optimal cutoff) were evaluated by ROC curve analysis. The consistency between 18F-FAPI PET/CT diagnosis and pathological diagnosis was assessed using the kappa test. A p-value <0.05 was defined as statistically significant.

Statistical analysis was performed using SPSS 17.0.

① Diagnostic performance evaluation, four-grid table index calculation:

Sensitivity = True positives / (True positives + False negatives) × 100%

Specificity = True Negative / (True Negative + False Positive) × 100%

Positive predictive value = true positive / (true positive + false positive)

Negative predictive value = true negative / (true negative + false negative)

② ROC curve analysis:

Calculate the area under the curve (AUC) and evaluate diagnostic performance (AUC>0.9 indicates excellent, 0.8-0.9 indicates good, 0.7-0.8 indicates moderate).

Determine the optimal cutoff for SUV using the maximum Youden index.

③ consistency check

The consistency between 18F-FAPI PET/CT and pathological diagnosis was evaluated using the Kappa coefficient.

Kappa>0.8: Excellent consistency;

0.6-0.8: High consistency;

<0.6: Consistency should be interpreted with caution.

Bilateral test, $p<0.05$ defined as significant difference.

④ survival analysis

Kaplan-Meier method:

Collect baseline PET parameters (lesion SUVmax, lesion SUVmean, MTV, LTV, bone marrow SUVmax, etc.), and plot PFS/OS curves according to treatment response (CR/PR vs. SD/PD), pathological response (e.g., MPR status), or PET parameter grouping (e.g., high/low SUVmax). Compare the significance of survival differences between groups using the Log-rank test ($p<0.05$).

Cox proportional hazards model:

Univariate analysis: Screening of clinical variables associated with PFS/OS (age, stage, SUVmax, MTV, etc.).

Multivariate analysis: Significant univariate variables ($p<0.1$) were included, with quantified hazard ratios (HR) and 95% confidence intervals.

Verify the proportional hazards assumption (Schoenfeld residual test).

8 Data Recording and Management

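### Survival time runs from diagnosis, but the PET groups exist only from the scan: OS curves are inflated for patients diagnosed earlier, and the PET hazard ratio can be biased either way

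*Protocol*

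**What the plan says.** Protocol 2.1.4 gives the only time origin in the document: "It tracks the time from diagnosis to specific events (e.g., CR, PR, SD, PD, recurrence, death) in lung cancer patients". The sentences after it name Kaplan-Meier curves and a multivariable Cox model.

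Protocol 7.3, survival analysis, sets the groups: "Collect baseline PET parameters (lesion SUVmax, lesion SUVmean, MTV, LTV, bone marrow SUVmax, etc.), and plot PFS/OS curves according to treatment response". Pathological response (for example MPR) is a second grouping, and the third is "or PET parameter grouping (e.g., high/low SUVmax", that is, a high and a low group. SUVmax and MTV also enter the Cox model as ordinary covariates. The section states no origin of its own and mentions neither delayed entry nor a landmark.

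Protocol 5.3.1 admits "Patients with suspected or confirmed lung cancer" and requires that "18F-FAPI PET/CT has been performed". No limit is set on time since diagnosis. Section 6.2 takes down "tumor history, surgical history, biopsy history, radiotherapy history, chemotherapy history" as history, and none of these is an exclusion in 5.3.2. Section 2.1.1 adds a use late in the disease: "the performance of this modality in early diagnosis, staging, and recurrence monitoring was analyzed".

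**The concern.** A prognostic marker can be related only to what happens after it is measured. Here the clock may start months or years before the measurement, and only people who lived to be scanned can enter.

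For OS this is uncorrected left truncation. The patient counts as at risk of death during an interval in which a death would have prevented enrolment. For PFS the fault differs: a previously treated patient may have progressed or recurred before the scan, so the outcome can come before the value meant to predict it.

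At stake is secondary endpoint 3, the prognostic value of the scan, which is also half of the study's stated purpose. The curves would look too good. The PET hazard ratio could reflect when patients were scanned rather than how their tumours behave.

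**Working it through.** The protocol gives no event rate, hazard ratio or median for PFS or OS, no share of already-confirmed patients and no diagnosis-to-scan interval. There is therefore no figure to reproduce, and every input below is an assumption shown over a range.

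**1. OS median, closed form.** Assume exponential survival with a true median of 24 months, so h = ln 2 / 24 = 0.02888 per month. A share f of analysed patients was already diagnosed, with an exponential delay of mean m months, kept only if alive at the scan. Among those kept, the delay is exponential with rate a = 1/m + h. Counting from diagnosis without delayed entry, and ignoring censoring, the curve is

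S(t) = (1 − f)·e^(−ht) + f·[a·e^(−ht) − h·e^(−at)] / (a − h).

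- m = 1, f = 0.3, t = 24.3: a = 1.0289, e^(−ht) = 0.4957, the bracket term is 0.5100, and S = 0.7 × 0.4957 + 0.3 × 0.5100 = 0.500. The naive median is 24.3; with f = 0.7 it is 24.7.
- m = 12, f = 0.7, t = 31.0: a = 0.1122, e^(−ht) = 0.4085, the bracket term is 0.5394, and S = 0.3 × 0.4085 + 0.7 × 0.5394 = 0.500. The naive median is 31.0; with f = 0.3 it is 27.1.

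Simulation with 6 to 42 months of follow-up after the scan gave the same picture: 24.3-24.7 and 26.8-31.1 months.

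**2. 24-month OS over a wider range.** Take the delay as exponential with mean m among those scanned (a = 1/m in the formula) and a true 24-month survival from the scan of 0.50. The bracket term is 0.601, 0.693 and 0.798 for m = 6, 12 and 24.

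- f = 0.25, m = 6: 0.75 × 0.5 + 0.25 × 0.601 = 0.525.
- f = 0.75, m = 24: 0.25 × 0.5 + 0.75 × 0.798 = 0.724.

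Simulation with censoring gave 0.53 to 0.73. With f = 0 there is no inflation.

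**3. Hazard ratio, large samples.** Same setting, f = 25-75%, mean delay 6-24 months, two PET groups, Cox model from diagnosis without delayed entry:

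| Delay and uptake | True HR 2.0 reads as | True HR 1.0 reads as |
|---|---|---|
| Unrelated | 1.99 down to 1.67 | about 1.0 |
| Mean delay halved in high uptake | 2.10 to 2.58 | 1.04 to 1.40 |
| Mean delay doubled in high uptake | 1.78 down to 1.04 | 0.93 down to 0.65 |

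Counting from the scan, or from diagnosis with delayed entry at the scan, returned about 2.0 and about 1.0 throughout.

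**4. Null effect at trial size.** n = 120 × 0.9 = 108, 50% already confirmed, uptake 0.5-1 SD lower in them, median split:

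- Mean delay 1-3 months: HR about 1.00-1.05.
- Mean delay 6-12 months: HR about 1.06-1.21.
- False-positive rate at a nominal 0.05: near nominal at 1-3 months, and up to about 0.09 at 12 months and 1 SD. Separate runs of that extreme case ranged from 0.09 to 0.12.

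The 108 treats every retained subject as having lung cancer. Suspected patients are enrolled too, so the number with cancer may be smaller.

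**The case against.** Section 2.1.4 describes study content. Its sentence lists response categories as events and does not name PFS or OS, and formal definitions are often left to an analysis plan that is not at hand. So the protocol states an unsuitable origin loosely rather than as a formal definition. It is still the only origin stated, it leads straight into the Kaplan-Meier and Cox text, and nothing in 7.3 replaces it.

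The word baseline in 7.3, with grouping by later response, fits scans taken close to diagnosis. At a 1-month mean delay the effect is indeed small. But no interval is fixed, and prior treatment and recurrence monitoring are in scope.

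Three stronger readings are tempting and are not supported.

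- A reader might infer that the whole pre-scan interval is guaranteed free of events. That is true of death only; earlier progression is not an exclusion.
- A reader might infer that the hazard ratios are biased in any case, or always away from 1. If delay is unrelated to uptake, a null effect stays null and a true one shrinks. A spurious effect needs delay and uptake to be related, and may go either way.
- A reader might infer that the problem reaches the main result. Sensitivity, specificity, accuracy and the sample size do not depend on the time origin.

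**Conclusion.** The point holds in limited form. Followed as written, the plan counts pre-scan survival as time at risk for every patient confirmed before the scan, and it lets a PFS event precede the PET measurement.

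The direction is certain for the OS curves: upward whenever such patients are included. For the PET hazard ratio, both the presence and the direction of bias depend on how delay relates to uptake and on whether a true effect exists.

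The size is known only moderately well. It is negligible if nearly all patients are scanned within about a month of diagnosis. It is several months of median OS, with an appreciable shift in the hazard ratio, if many are scanned a year later. These figures assume exponential survival and delays, and the protocol supplies neither the confirmed share nor the delay. Because only a secondary endpoint is touched, this should be corrected but does not threaten the primary analysis.

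**What to change.** In 2.1.4 and 7.3, state that PFS and OS start at the date of the baseline 18F-FAPI PET/CT, meaning the first study scan, since post-treatment reassessment may bring further scans. Count only progression after that scan as a PFS event. If OS from diagnosis is wanted, keep that origin with delayed entry (left truncation) at the baseline scan.

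A scan-date origin does not repair the CR/PR versus SD/PD and MPR groupings, because these are known only after treatment. For them, start the clock at a landmark when response is assessed and include only patients still at risk then.

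The cost is a few sentences and no added patients or visits. The protocol does not list the scan date as a data item, but every subject must have had the scan, so it should be available from the imaging system. The downside is that reported survival times become somewhat shorter, and patients with an event before the landmark leave the response comparisons.

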1.3 Current Challenges

1.3.1 The diagnostic efficacy of 18F-FAPI PET/CT in different lung cancer subtypes requires further validation

Although existing studies have demonstrated the significant efficacy of 18F-FAPI PET/CT in certain tumor types, its diagnostic performance across different lung cancer subtypes remains to be further validated. Significant biological and clinical differences exist among various lung cancer subtypes, particularly non-small cell lung cancer (NSCLC) and small cell lung cancer (SCLC). Research indicates that the clinical validation of 18F-FAPI PET/CT for identifying lung cancer subtypes has not been sufficiently established. For instance, one study revealed that the sensitivity and specificity of 18F-FAPI PET/CT in detecting lung cancer differ from those of conventional 18F-FDG PET/CT, especially regarding tumor burden and metabolic activity across different subtypes [6]. Therefore, the specific diagnostic capabilities for various lung cancer subtypes still require validation through large-scale clinical trials.

1.3.2 Consistency of Imaging Evaluation Criteria in the Assessment of Treatment Efficacy for Lung Cancer

Currently, the most commonly used imaging evaluation standard is the Response Evaluation Criteria in Cancer (RECIST 1.1), which primarily relies on unidimensional measurements of tumor size. However, the limitation of RECIST 1.1 lies in its failure to adequately account for the biological characteristics of tumors and the complexity of treatment responses. For instance, the introduction of immunotherapy has made tumor response patterns more complex, potentially leading to temporary increases in tumor volume, which may be misinterpreted as disease progression under the traditional RECIST criteria. Consequently, 18F-FAPI PET/CT-based evaluation standards such as iRECIST have emerged to better reflect the efficacy of immunotherapy and account for the dynamic changes in tumor responses [7].

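### The prognostic log-rank has no stratification factor and the Cox model takes covariates only through a p<0.1 screen, so nothing guarantees that an SUVmax–survival association is separated from cell type

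*Protocol*

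**What the plan says.** All references are to the protocol.

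- **Population.** Section 5.3.1 admits "Patients with suspected or confirmed lung cancer", with no limit on cell type.
- **Subtypes.** Section 1.3.1 states: "Significant biological and clinical differences exist among various lung cancer subtypes, particularly non-small cell lung cancer (NSCLC) and small cell lung cancer (SCLC"). It also mentions differences between FAPI and FDG imaging, "especially regarding tumor burden and metabolic activity across different subtypes".
- **Use of histology.** Section 2.1.3 plans subgroups "stratified by disease pathological type (adenocarcinoma/squamous cell carcinoma/small cell lung cancer"), for a diagnostic purpose: "The aim was to evaluate the differences in sensitivity and specificity of 18F-FAPI PET/CT across different patient populations".
- **Survival comparison.** Section 7.3 ④ draws PFS/OS curves by treatment response, by pathological response, "or PET parameter grouping (e.g., high/low SUVmax"), and compares groups by log-rank at p<0.05. It gives no stratification factor.
- **Cox model.** Section 2.1.4 says: "Cox proportional hazards model multivariate regression quantifies the contribution of factors such as age and pathological stage to survival risk". Section 7.3 ④ describes the univariate step as "Screening of clinical variables associated with PFS/OS (age, stage, SUVmax, MTV, etc".) and carries forward variables with p<0.1. It forces no variable in, and it plans a Schoenfeld residual check.

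**The concern.** Cell type can confound the SUVmax comparison if it is related both to uptake and to survival. The protocol's own background makes this plausible, and its diagnostic analysis already separates the cell types. The prognostic analysis has no matching step. The log-rank is unadjusted as written, and the Cox model adjusts for histology only if someone adds it to the candidates and it then passes the screen.

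At stake is the reading of secondary endpoint ③. A survival difference between high and low SUVmax might be partly a difference between cell types, which pathology (the gold standard in section 5.2.2) already provides without the scan. The distortion can go either way. If the cell type with worse survival has higher uptake, the hazard ratio for high SUVmax rises. If it has lower uptake, the ratio falls and can hide a real adverse effect.

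**Working it through.** **Plan figure to reproduce.** There is none for this analysis. The 113 and 120 in section 7.1 are for the diagnostic endpoint, and no event count, hazard ratio or power is stated for prognosis.

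**Inputs from the protocol.** 120 patients less 10% loss: 120 × 0.90 = 108. Two-sided α = 0.05. Entry rule p<0.1.

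**Assumed inputs.** Share of small cell cancer (SCLC), its hazard ratio against other types, and the share of SCLC falling in the low SUVmax half. SUVmax has no effect of its own. Stage is split 50:50 with hazard ratio 2 and is independent of histology. Survival is exponential, with uniform censoring at 6–48 months and about 55 events.

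**1. False-positive rate and hazard ratio (high v low SUVmax), 1,500 runs per setting.**

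| SCLC share, HR, share in low half | Log-rank, unstratified | Log-rank, stratified | Cox with stage and age: rejection, HR | Same Cox, stratified by histology |
|---|---|---|---|---|
| 15%, 2.0, 70% | 6.0% | 5.2% | 6.8%, 0.91 | 5.9% |
| 15%, 2.5, 75% | 7.9% | 5.4% | 8.5%, 0.87 | 5.7% |
| 20%, 2.5, 75% | 10.8% | 6.5% | 10.9%, 0.84 | 5.2% |

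The stratified Cox hazard ratio is 0.99–1.00 throughout. The Monte Carlo standard error near 6% is √(0.06 × 0.94 / 1,500) = 0.6 percentage points, so the first row alone shows little in the rejection rates. A separate set of 4,000 runs per setting (55–60 events) gave 5.1–9.5% for the unstratified log-rank, with hazard ratio 0.98–0.84, against 4.8–5.7% and about 1.00 when stratified. Taken together, the assumed settings give about 6–10%. If SCLC sat in the high half instead, 0.93–0.84 would become roughly 1/0.93 = 1.08 to 1/0.84 = 1.19.

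**2. Sensitivity to the assumptions.** A different model used 65/25/10% adenocarcinoma/squamous/small cell, 108 patients, about 43–49 events and 4,000 runs. Hazard ratios by type are in that order. Uptake shifts relative to adenocarcinoma are in SD.

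| Setting | Unstratified rejection | HR |
|---|---|---|
| HR 1/1.5/3, no uptake difference | 5.1% | 1.00 |
| HR 1/1.3/2, both types +0.5 | 5.1% | 1.07 |
| HR 1/1.5/3, both types +0.8 | 9.7% | 1.18 |
| HR 1/2/4, both types +1.0 | 19.1% | 1.36 |
| HR 1/1.5/3, squamous +0.8, small cell −0.8 | 5.6% | 0.95 |

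Stratified by histology, rejection is 4.5–5.7% and the hazard ratio 0.99–1.01 in every row. The bias matters only when uptake and hazard differ clearly in the same direction.

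**3. Would histology survive the p<0.1 screen?** Approximate SE(log HR) = 1/√(d·q·(1−q)), with d events and SCLC share q. The probability of failing the screen is about Φ(1.645 − ln HR / SE). Take d = 57.5, the middle of 55–60. For q = 0.15 and HR 2.0, SE = 1/√(57.5 × 0.1275) = 0.369, z = 0.693/0.369 = 1.88, and Φ(−0.23) = 41%.

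| SCLC share, HR | Formula | Simulated (3,000 runs) |
|---|---|---|
| 10%, 2.0 | 53% | 48% |
| 15%, 2.0 | 41% | 38% |
| 15%, 2.5 | 20% | 17% |
| 20%, 2.5 | 13% | 11% |

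A real cell-type effect is therefore often dropped. When histology is at least screened, however, the SUVmax test in those runs stayed near nominal (4.4–6.0%, HR 0.98–0.99), because the screen tends to keep histology where it matters most.

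**4. Power.** With a true SUVmax hazard ratio of 2, unstratified v stratified power was 75% v 76% without confounding and 55% v 74% with it.

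**The case against.** The strongest reply is that the protocol excludes nothing. Section 2.1.4 gives its factors as examples, and the list in section 7.3 ends in an open et cetera. A reader might infer that all cell types are pooled in one Cox model adjusted only for age and stage. The text does not say that: it describes univariate screening followed by a multivariable model, it names SUVmax and MTV too, and high/low SUVmax is one example among several groupings. This part of the objection stands.

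A second reply is that covariates and strata belong in the statistical analysis plan, which is not shown. That is partly right. Yet section 7.3 does fix the test, the kind of grouping and the entry rule. The open lists concern the Cox model and do not reach the log-rank, and a later plan that followed the p<0.1 rule would still not guarantee adjustment.

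Third, the link of histology with both uptake and survival is not quantified anywhere. Section 1.3.1 says that performance by subtype still needs validation, and section 2.1.3 sets out to evaluate differences without asserting them. This stands, and it makes the size conditional. The simulations also treat all 108 patients as having lung cancer, although suspected cases are eligible, and they let stage absorb none of the confounding.

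A reader might also infer that a Cox model with mixed cell types does not fit this cohort. Nothing here shows that. The simulations used constant hazard ratios and did not test fit, and section 7.3 plans a check of proportional hazards.

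**Conclusion.** The point holds as a minor one. As written, the PET-parameter log-rank is unadjusted for cell type in a cohort of mixed cell types, and the Cox entry rule does not secure adjustment. Under the assumed 15–20% SCLC, hazard ratio 2.0–2.5 and 70–75% sorting into one SUVmax half, false-positive findings rise from 5% to about 6–10% and the hazard ratio moves from 1.00 to about 0.93–0.84. Milder or opposing patterns leave almost no bias; a strong pattern gave 19%. Neither size nor direction can be settled from the protocol. The main exposure is the unstratified log-rank and a Cox model that never considers histology; the screen by itself does little harm to the SUVmax test once histology is a candidate.

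**What to change.** In sections 2.1.4 and 7.3 ④:

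- Stratify the log-rank for PET-parameter groups by histology, at least SCLC versus NSCLC, with adenocarcinoma and squamous cell carcinoma separated where numbers allow.
- Stratify the multivariable Cox model by histology, or force histology into it, regardless of the p<0.1 screen.
- Name the SUVmax hazard ratio from that model as the prognostic result.

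The cost is wording. Section 2.1.3 already requires pathological type, so no data are added. The power runs show no loss from stratifying, although an SCLC stratum may be small: 15% of 108 is about 16 patients. The change should be made before survival data are examined.
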